The project utilizes a software (REDCap) which randomizes individuals into intervention and control groups, using permuted block randomization. As participants enroll in the study, they will be given a study identification number (e.g. 1,2,3). Both the intervention and control groups will complete baseline surveys.

Control group participants will receive standard care and will be expected to return to Adelante Healthcare Mesa to receive the additional HPV vaccine booster doses. Intervention group participants will be referred to receive the additional HPV vaccine doses at their community pharmacy. At post-intervention, intervention participants will be asked if their children completed the HPV vaccine series.

Primary behavioral outcome: At the end of the 16-month intervention, PI will ask clinic staff to report HPV vaccination dose completion (for vaccine doses 1,2,3) for all study participants.

Follow-up Survey Data Collection: RA will call all participants and administer follow-up survey to measure potential changes in DOI theoretical constructs (see baseline survey).

Qualitative telephone in-depth interviews: To qualitatively explore intervention feasibility and acceptability, PI will conduct telephone interviews with patients, patients' caregivers, clinic primary care providers, and clinic pharmacists.

- In-depth interview with Caregivers and/or Young Adult Patients: PI will conduct telephone interviews with caregivers from the control group (standard care) and from the intervention group (pharmacist-administered HPV vaccination) related to their experiences taking part in the study.
- In-Depth interviews with Providers and Pharmacists: Researchers will conduct telephone interviews with all the clinic's participating primary health care providers and office manager (n= 4) and local pharmacists who work at pharmacies where patients were referred to receive the HPV vaccine (n=4) to explore their acceptability and perceived feasibility of the intervention. They will be asked how the intervention impacted the quality of patient care, ways in which the intervention impacted patient flow within the clinic, how satisfied they were with the intervention, and perceived fit of the intervention within their workplace.

Participant Incentives: Research participants will receive e-gift card incentives (of their choosing from Tango Card, Inc) for completing study surveys (\$20 dollars per survey completed) and for participating in telephone interviews (\$30).

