PI will submit the interview audio-recordings to an ASU-approved transcription company. Using the interview guide to determine a priori themes, PI will create a coding book for the interview data. Reading through all interview transcripts, PI will add emerging themes to expand the coding guide. PI will train the RA in descriptive content analysis. They will review and code one transcript together, code an additional three transcripts separately, meet to discuss coding choices, and reach an agreement on data interpretations and analysis before they split the remaining interview transcripts for review. PI and RA will upload all transcripts and codes into ATLAS.ti software. PI will take the outcomes from the analyses from ATLAS.ti and begin to summarize findings for each in-depth interview question with the RA to ensure interpretation consensus and create a comprehensive summary of the findings related to intervention acceptability and feasibility.

Data Storage:

Patients' information will be de-identified and given a unique Participant Study Number for data analysis by an Adelante Healthcare Mesa healthcare practitioner. All signed informed consent documents will remain with the PI. She will secure them in a locked drawer of a locked office. These forms will be kept up to two years and will be destroyed at the end of those two years.

17 Safety Monitoring

[name] (PI) and the research assistants will meet on a monthly basis to evaluate the data collected for the study. They will review completeness of patient surveys and informed consent and updates related to HPV vaccine series completion.

18 Consent Process

The clinic will notify the RAs when potential participants have scheduled office visits. After the office visit, a nurse or office staff member will walk the patient to the RA's research office. The RA will briefly explain that this study is about HPV vaccine intentions and vaccine completion and invite caregivers to sign up for the study. If patients decide not to sign up that day, they will be given a study information sheet and a phone number to call should they decide to participate later. RA will also write down their contact information to follow up on study enrollment. For caregivers interested in signing up for the study, the RA will administer the informed consent and baseline surveys.

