The project biostatistician will have already generated a randomization table for the intervention and control groups, using permuted block randomization. As participants enroll in the study, they will be given a study identification number (e.g. 1,2,3). Based on their study number and the randomization table, they will be assigned to either intervention or control group.

For the in-depth interviews with caregivers (at post-intervention), the RA will contact participants via phone. The RA will administer informed consent via the phone and verbally consent participants prior to conducting the phone interviews.

19 Investigational New Drug or Devices

NA

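### Sections 8 and 18 describe randomisation in two unreconciled ways, and neither says how the next assignment is kept from the staff who enrol

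*Combined protocol and SAP*

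**What the plan says.** Section 8 (Procedures Involved) gives the task to software: "The project utilizes a software (REDCap) which randomizes individuals into intervention and control groups, using permuted block randomization". It mentions neither a table nor the biostatistician.

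Section 18 (Consent Process) gives a different account. "The project biostatistician will have already generated a randomization table for the intervention and control groups, using permuted block randomization". Numbers are then issued one by one ("As participants enroll in the study, they will be given a study identification number (e.g. 1,2,3"), and the number decides the arm: "Based on their study number and the randomization table, they will be assigned to either intervention or control group". REDCap is not mentioned there.

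On who enrols, Section 6 has the research assistant screen callers. Section 18 has the same role explain the study, invite the caregiver and complete entry: "For caregivers interested in signing up for the study, the RA will administer the informed consent and baseline surveys". Caregivers may also put off the decision ("If patients decide not to sign up that day, they will be given a study information sheet and a phone number"), and the research assistant keeps their contact details to follow up.

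On who issues the study number, Section 18 is silent. Section 16 refers to participants being "given a unique Participant Study Number for data analysis by an Adelante Healthcare Mesa healthcare practitioner", in a sentence about de-identification. It is not clear whether this is the number that fixes the arm.

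No section states a block size, randomisation strata, who holds the list, or any concealment or blinding measure.

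**The concern.** Randomisation protects the comparison only if the person deciding whether and when to enrol a family cannot tell which arm comes next. A list read off by consecutive study number is weak on this point unless someone outside enrolment holds it. Anyone who sees the list knows the next arm, and anyone who tracks past arms and knows the block size can often work it out.

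The setting makes this more than a formality. There is one clinic. Arm is evident in practice, because intervention families are referred to a pharmacy and control families return to the clinic, so past assignments are likely to become known. The order of enrolment is flexible, because caregivers may defer and be followed up.

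The primary outcome, series completion, plausibly depends on how motivated the family is. Section 16 compares the arms with a two-proportion Z test, which is unadjusted. The regressions in the same section look for factors associated with completion and are not specified as adjusting the arm comparison. If motivated families were steered towards one arm, the primary result would carry the bias.

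**Working it through.** **Step 1. The two descriptions side by side.**

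| Item | Section 8 | Section 18 |
|---|---|---|
| What makes the assignment | REDCap | Study number looked up in a table |
| Who prepares the list | Not stated | Biostatistician, in advance |
| Method | Permuted blocks | Permuted blocks |
| Block size, strata | Not stated | Not stated |
| Who holds or reads the list | Not stated | Not stated |
| Hidden from enrolling staff | Not stated | Not stated |

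The method agrees and the mechanism differs. No sentence says that the table is the list REDCap applies, and none says that it is a separate document.

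**Step 2. Order of events.** Section 18 describes consent and the baseline survey first, then the number and the assignment. Section 8 names the software and then says that both groups complete baseline surveys, with no wording that puts one before the other.

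**Step 3. How predictable the sequence could be.** The plan gives no figure to reproduce here. The only inputs from the documents are 90 participants, 45 per arm (Section 5), and permuted blocks. The block sizes below are assumptions.

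*Case A: enrolling staff can see the table.* All 90 of 90 assignments can be known in advance.

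*Case B: the table is hidden, but staff know every past assignment and a fixed block size of 2m.* Two quantities follow for 1:1 blocks:

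- Share known with certainty (one arm's places in the block are used up): 1/(m+1).
- Share guessed correctly by always naming the arm with more places left, with a coin toss at ties: [m − 1/2 + 2^(2m) / (2 × C(2m, m))] / (2m).

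Blocks of 4 (m = 2), by enumeration. Up to swapping the arm labels there are three sequences.

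- AABB: 2 certain; expected correct guesses 0.5 + 0 + 1 + 1 = 2.5.
- ABAB: 1 certain; 0.5 + 1 + 0.5 + 1 = 3.0.
- ABBA: 1 certain; 0.5 + 1 + 0.5 + 1 = 3.0.

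Certain: (2 + 1 + 1)/3 = 1.333 per block, and 1.333/4 = 33.3%. Correct: (2.5 + 3.0 + 3.0)/3 = 2.833 per block, and 2.833/4 = 70.8%. Both agree with the formulas.

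| Assumed block size | Certain | Certain, of 90 | Guessed correctly | Guessed, of 90 |
|---|---|---|---|---|
| 2 | 50.0% | 45 | 75.0% | 67.5 |
| 4 | 33.3% | about 30 | 70.8% | about 63.8 |
| 6 | 25.0% | 22.5 | 68.3% | 61.5 |
| 8 | 20.0% | about 18 | 66.6% | about 59.9 |
| 10 | 16.7% | 15 | 65.3% | 58.8 |

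An unpredictable sequence would give 50%, or 45 of 90, by guessing. Blocks of 4 and 8 do not divide 90 (remainder 2), so those counts are approximate. If randomisation were stratified, the shares would apply within each stratum.

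**The case against.** The strongest reply is that the two sections may describe one process: the biostatistician makes the list and the software applies it. Both sections use permuted blocks and the same sentence on study numbers. This stands. A reader might infer that the descriptions are incompatible, but the documents show only that they are not linked.

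A reader might also infer that allocation is not concealed. The documents do not say so. They name the author of the table but not who holds or reads it, and a list that fixes assignments in advance can still be fully concealed. Concealment is unspecified, not shown to be absent.

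A third tempting inference is that Section 8 randomises before the baseline survey, so that baseline attitude scores could be affected by arm. Section 8 only says who completes the surveys, and Section 18 places them before assignment. The text gives no support for an effect on baseline scores. The order in Section 18 lessens the risk but does not remove it, because a predictable next arm can still influence whom staff invite and when.

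Finally, steering requires that the research assistant knows or can guess the next arm, which no section states. Deferral is the caregiver's choice. This is also a pilot assessing preliminary efficacy, so the gap weighs less than in a confirmatory trial. These points limit the severity. They do not supply the missing safeguard.

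**Conclusion.** The point holds as a gap in the specification with a real risk attached. Sections 8 and 18 give two unreconciled accounts of how an arm is assigned, and no safeguard for the next assignment is described. It goes beyond missing detail, because following Section 18 as written would tie each assignment to a number that is apparently sequential.

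The size can be stated only conditionally. With a visible table, every assignment is known. With a hidden table, a fixed block size known to staff and all past assignments known, between 33% (blocks of 4) and 17% (blocks of 10) are certain, and between 71% and 65% can be guessed. These figures measure predictability, not bias. A reader might want to turn them into a shift in the difference between arms. That would need completion rates for likely and unlikely completers and a number of steered families, and the documents support no values for these.

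The conclusion rests on two readings of the text: that the example numbers mean sequential issue, and that arm is evident in practice, which is a strong inference in the absence of any blinding statement. The change should be made before enrolment. No breach is shown.

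**What to change.** Use one description, the same in both sections:

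- The biostatistician generates the list, with randomly varied block sizes that are not disclosed to research assistants or clinic staff.
- The list is loaded into REDCap, and research assistants and clinic staff cannot view it.
- REDCap releases each assignment only after eligibility, consent and the baseline survey have been recorded.
- Assignment by study-number lookup is removed from Section 18. The study number remains an identifier only, and Sections 16 and 18 say who issues it.
- Any randomisation strata are stated, or their absence is stated. Section 2 describes stratified recruitment, which is a different matter.

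If an exact 45:45 split is wanted, the varied blocks should be chosen to add up to 90.

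The cost is small: protocol wording and the set-up of a list in software the plan already names, with no added participants. This assumes that the site's REDCap set-up can withhold the list and release assignments one at a time, which the documents do not describe and the study team should confirm.
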